# Taiwan "Aerosol Box" versus UMMC "Intubation Box" : Clinical evaluation of the "Intubation Box" for ease of intubation

### **Background:**

Intubation is classified as an aerosol-generating procedure (AGP). Intubation in a confirmed COVID-19 patient with a high viral load poses a high risk of exposure to health care workers (HCW). To reduce this risk, the HCW and their assistants are advised to don full personnel protective equipment (PPE) with a powered air purifying respiratory (PAPR) during intubation. In view of this concern, this procedure is highly recommended to be done in a negative pressure room to control the spread of aerosolizing particles in the room. A first-pass success in intubation is also crucial to minimize the risk of infection to health care workers involved.

#### **Introduction:**

An Aerosol Box (from here on known as Box A) was recently designed by [name] Yung from Taiwan which adds extra protection to the intubator and the surrounding environment (Everington, 2020). The Aerosol Box is a transparent box made of acrylic or transparent polycarbonate sheet, designed with an opening on one side allowing it to fit over the patient's chest and neck, while the opposing side has two holes through which the intubator can insert their hands through (Figure 1). It was shown that this barrier enclosure during intubation protects the laryngoscopist. Canelli et al simulated a patient with a cough during intubation with and without the Aerosol Box. With the box, they showed that the simulated cough resulted in contamination of only the inner surface of the box, the laryngoscopist's gloves and gowned forearms. Examination of the laryngoscopist and the room with ultraviolet light after the simulated cough also showed no macroscopic contamination outside the box. In contrast, intubation without the box demonstrated that the laryngoscopist's gown, gloves, face mask, eye shield, hair, neck, ears, and shoes were all contaminated.

Feedbacks from our colleagues stated that intubation with Box A is slightly difficult and may cause delay in intubation. Canelli et al also concluded this observation. We, therefore, innovated the design of Box A to facilitate the laryngoscopist, as shown in Figure 2 ("Intubation Box", from here on known as Box B). We find that Box B has better ergonomics, and this will increase the rate of success of intubation.

### **Objectives:**

We aim to compare the relative intubating efficacies of these two boxes. This study assesses the time to successful intubation as the primary outcome. Our secondary outcomes will be the quality of the laryngoscopy view (objectively defined as "percentage of glottic opening" / POGO) and ease of intubation.

### Methodology:

This is a prospective randomized cross over trial to compare the time for intubation using these two devices by our anaesthetists. The planned duration from planning to recruitment to completion of study will be from 1st May 2020 to 31st December 2020. We will recruit eligible anaesthetists after obtaining written informed consent. The anaesthetist should have more than 5 years of experience with intubation as well as experience with intubating patients using videolaryngoscope for more than 20 times.

The anaesthetist will be randomised to intubate the manikin in either Box A or Box B first. The primary endpoint which is the time to successful intubation (defined as the interval from insertion of the laryngoscope blade into the mouth to inflation of the tracheal tube cuff) will be recorded. Other endpoints are the numbers of intubation attempts (each attempt defined as complete removal of video laryngoscope from mouth and reinsertion) will be recorded. Failed insertion is defined as the entire intubation procedure taking more than 120 seconds or more than 3 insertion attempts.

The participants will evaluate their intubation experience using both boxes with a questionnaire based on the ISO9421-11 standard, that is effectiveness, efficiency and satisfaction.

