### Sample size:

The primary endpoint of the study is time to successful tracheal intubation. Sample size is based on a calculation of 10.0 s as the clinically relevant difference in intubation time, with a prospective power analysis at 80% power and 0.05 level of significance. It shows that a sample of 28 laryngoscopists would be required. This will be a cross over study, hence we will recruit 30 laryngoscopists to also account for dropouts and protocol breaches. In view that the time to successful intubations data are not normally distributed, we will use the Mann Whitney U test to analyse intubation times. Categorical data such as number of intubation attempts will be evaluated for differences among the groups using the chi-square test. All statistical analyses

will be performed using IBM SPSS statistics 23 database. A value of p < 0.05 is considered significant.

[figure not shown]

Figure 1 (Box A). Dimensions are 50 cm by 50 cm (height x width), with a thickness of 40 cm. (Source: https://sites.google.com/view/aerosolbox/design)

[figure not shown]

Figure 2 (Box B). Dimensions are 46 cm x 58 cm (height x width) with a thickness of 51cm. The upper portion of the box facing the intubator is made slanted at a 150 degree angle hence providing better ergonomics to the intubator. The curved design at one end of the box is to accommodate the obese/big build patient whose shoulder breadth may be wider than the box's width.

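### Box order is randomised, but the planned tests use neither sequence nor period and no balanced order is stated: a minor weakness that is cheap to remove

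*Combined protocol and SAP*

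**What the plan says.** All of this is in the combined protocol and SAP.

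- **Design (Methodology).** A randomised crossover of two intubation boxes on a manikin: "The anaesthetist will be randomised to intubate the manikin in either Box A or Box B first". No ratio, blocking, practice run or period assessment appears in the readable text.
- **Eligibility (Methodology).** More than 5 years of intubation experience, and "experience with intubating patients using videolaryngoscope for more than 20 times". No experience with either box is required.
- **Analysis (Sample size).** For the primary endpoint, "we will use the Mann Whitney U test to analyse intubation times". For the rest, "Categorical data such as number of intubation attempts will be evaluated for differences among the groups using the chi-square test". Sequence, period and order are not mentioned.
- **Size (Sample size).** 28 operators for a 10.0 s difference at 80% power and 0.05 significance; "hence we will recruit 30 laryngoscopists to also account for dropouts and protocol breaches".
- **Data collection sheet.** Results are entered under one column per box, for direct laryngoscopy and for videolaryngoscopy. No field for which box came first is visible.
- **Not readable.** The flow chart and Appendix B have headings only, so allocation details or a record of order could be there.

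**The concern.** Randomising order guards against a practice effect, but the analysis then makes no use of it. Some practice effect is plausible because both boxes are new. The Introduction says "An Aerosol Box (from here on known as Box A) was recently designed by" its Taiwanese originator, and of Box B, "We, therefore, innovated the design of Box A to facilitate the laryngoscopist". An operator used to the laryngoscope may still need one attempt to get used to working through a box.

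A gain on the second box would have two consequences. With equal numbers in each order it cancels from the average box difference but adds variability, which costs power. With unequal numbers it no longer cancels, and part of it is read as a box effect. If the order were recorded nowhere, it could not be adjusted for afterwards.

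**Working it through.** **The plan's own figure.** The 28 cannot be reproduced because no standard deviation is given. Solving back with a paired design, 10 s, 80% power and two-sided 0.05 (sidedness is assumed), the normal formula gives SD_diff = 10 × √28 / (1.960 + 0.842) = 18.9 s. The noncentral t version gives 18.2 s, which is used below. It is an inferred value, not one from the plan.

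**Shift.** Let g be the first-use time minus the second-use time, nAB the number using Box A first, nBA the number using Box B first, and n = 30. Ignoring period, the estimated A-minus-B difference moves by g × (nAB − nBA)/n. The values of g are assumptions.

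- 15:15 gives zero.
- 19:11 gives 8/30 = 0.267, so 1.3 s at g = 5 s and 2.7 s at g = 10 s.
- If order were allocated by simple randomisation (Binomial(30, 0.5)), the mean |nAB − nBA| is 4.33. As a fraction this is 4.33/30 = 0.144, so the expected absolute shift is 0.7 s at g = 5 s and 1.4 s at g = 10 s. The chance of 19:11 or worse is 20%.

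In simulation at 19:11 with a true difference of 10 s and within-operator correlation 0.25, the unadjusted Hodges-Lehmann estimate was 11.4 s (g = 5) and 12.8 s (g = 10). The sequence-based estimate proposed below gave 10.1 and 10.0 s.

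**Added noise at 15:15.** Half the operators have their A-minus-B difference raised by g and half lowered by g. The SD of the differences becomes √(18.21² + g²): 18.9 s at g = 5, 20.8 s at g = 10 and 23.6 s at g = 15.

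**Power.** Simulated with 30 operators at 15:15, a true difference of 10 s, normal times and two-sided 0.05. The SD of a single time is 18.21/√(2(1 − ρ)), where ρ is the within-operator correlation.

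| Test | g = 0 | 5 s | 10 s | 15 s |
|---|---|---|---|---|
| Planned Mann-Whitney, ρ = 0 | 82% | 81% | 78% | 72% |
| Planned Mann-Whitney, ρ = 0.25 | 73% | 72% | 68% | 62% |
| Planned Mann-Whitney, ρ = 0.5 | 54% | 53% | 50% | 45% |
| Signed-rank, any ρ | 81% | 79% | 72% | 59% |
| First-minus-second difference compared between sequences | 79–80% | 79–80% | 79–80% | 79–80% |

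Reading along the rows, learning costs the planned test about 1 point at 5 s, 4 at 10 s and 9 to 11 at 15 s. The drop from one planned-test row to the next comes from ignoring the pairing, which is a separate matter and is not counted here. Beyond pairing, using the sequence is worth −2, 0, +8 and +21 points across the four gains.

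**False positives of the planned test.** Averaged over simple randomisation, at ρ = 0, 0.25 and 0.5, they are 5.5%, 2.8% and 0.9% for g = 5 s, and 6.5%, 3.8% and 1.5% for g = 10 s. Given a 19:11 split and g = 10 s, they are about 9% at ρ = 0 and 2% at ρ = 0.5. The sequence-based test stays between 4% and 5%.

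**The case against.** The strongest reply is that all the harm depends on a practice effect the documents do not quantify. The operators are experienced. An assumed 10 s gain is as large as the whole clinically relevant difference, and 15 s exceeds it. At 5 s the expected shift is 0.7 s, the planned test loses 1 power point, and using the sequence adds nothing beyond pairing. This stands, and it sets the severity.

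Three stronger readings are tempting and not supported:

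- *The plan is biased or inflates false positives.* The shift averages zero over randomisations, and the averaged error rate is below 5% in four of the six cells and at most 6.5%. The harm belongs to one unlucky split.
- *Allocation and order are missing from the trial.* The flow chart and Appendix B cannot be read. The only firm statement is that the readable text does not give them. The statistical text itself is readable and uses neither term.
- *A simple paired test would be worse than the plan.* Signed-rank loses more to learning, but its power is higher than the planned test's in seven of the eight cells with positive correlation.

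Two limits of the calculation also stand. The form records two laryngoscopes per box, so up to four intubations per operator, while the simulation has two; its learning figures need not hold for the second laryngoscope. And the sequence-based test is not always the stronger. The plan says "Failed insertion is defined as the entire intubation procedure taking more than 120 seconds or more than 3 insertion attempts", without stating how failures enter the analysis of times. With assumed skewed times, ρ = 0, no learning and 3% failures per box set to 120 s, its power is 69% against 78% for the planned test. Under the same model at ρ = 0.5 it is 68% against 49%, an advantage due to pairing.

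**Conclusion.** The point holds as a minor one. The analysis ignores the sequence that the design randomises, and no balance of order is stated in the readable text. Learning would add noise, and with an unequal split it would move the box difference: by 1.3 s (5 s gain) to 2.7 s (10 s gain) at 19:11, against a 10 s target. At gains of 5 s or less the effect is small; at 10 to 15 s the loss of power becomes material. These sizes rest on assumed gains, a back-solved SD of 18.2 s and, for the chance of imbalance, simple randomisation. The protocol does not say that simple randomisation will be used. A reader should not infer a systematic bias in favour of either box.

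**What to change.** 1. Allocate order in blocks to 15 A-first and 15 B-first, and say so in Methodology. If the flow chart or Appendix B already does this, a cross-reference is enough. Balance matters for the adjusted analysis too: with 28 operators, the power of a period-adjusted test falls from about 80% when balanced to 76% at 18:10 and 71% at 20:8.
2. Record the intubation order beside each time on the data collection sheet.
3. Make the primary analysis of times a within-operator comparison that uses the randomised sequence. For example, compare first-box minus second-box times between the A-first and B-first groups by Mann-Whitney, and report half the Hodges-Lehmann shift as the box difference in seconds. Give an unadjusted signed-rank test as a sensitivity analysis.

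**Cost.** A blocked list, one number beside each time and one analysis paragraph; no extra operators or intubations. With no learning, the sequence-based test gives up about 2 power points against signed-rank, and about 3 against the planned test if within-operator correlation is zero. It gives up more if failed intubations receive an extreme value and correlation is near zero. It removes an average period effect but not unequal carry-over between boxes, which is possible if some operators already know Box A.

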# MILESTONES AND DATES CHART PROJECT TITLE: TAIWAN "AEROSOL BOX" VERSUS UMMC "INTUBATION BOX": CLINICAL EVALUATION OF THE "INTUBATION BOX" FOR EASE OF INTUBATION

									YEA	R 202	0							
	Apr	Apr	Ma	May	June	June	Jul	Jul	Aug		Sept	Sept	Oct	Oct	Nov	Nov	Dec	Dec
	1-	16-	у	16-	1-15	16-	1-	16-	1-	16-	1-	16-	1-	16-	1-	16-	1-	16-30
	15	30	1- 15	31		30	15	31	15	31	15	30	15	31	15	30	15	
ACTIVITIES			13															
Submission for ethics committee approval																		
Preparation of resources required																		
Data collection																		
Data entry																		
Data analysis																		
Writing of report																		
Submission of completed paper to ISI journal																		

Part 1: User profile			
Name:			
Professional category:	:		
Anaesthesia experienc	ce:		
Age:			
Gender:			
Part 2: Intubating co	onditions pr	ofile	
For direct laryngoscop	-		
		T-: D	HMMC D
Findings Time for successful		Taiwan Box	UMMC Box
(seconds)	IIIIuoaiioii		
Number of intubatio	n attempts		
POGO grading (%)			
Cormack Lehane gra	ade (1-4)		
For videolaryngoscop	y:		
Findings		Taiwan Box	UMMC Box
Time for successful		Turwun Don	CHAIC BOX
(seconds)			
Number of intubation	n attempts		
POGO grading (%)			
Cormack Lehane gra	ide (1-4)		
Part 3: Usability pro	file		
In this section, we wo		now the usability of this eq	uipment (Taiwan Box vs UMMC Box)
during intubation.			
When using for intul	hation with	direct laryngoscopy:	
Findings	vativn With	Taiwan Box	UMMC Box
On a scale of 0-			
10, how easy was	0	10	0

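### No rule says how a failed intubation enters the primary Mann-Whitney comparison of times; leaving failed runs out would favour Box A if, as the plan expects, it succeeds less often and its failed runs are its slower ones

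*Combined protocol and SAP*

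**What the plan says.** - **Endpoint.** The Objectives state: "This study assesses the time to successful intubation as the primary outcome". The Methodology times it as "defined as the interval from insertion of the laryngoscope blade into the mouth to inflation of the tracheal tube cuff".
- **Failure.** The Methodology adds: "Failed insertion is defined as the entire intubation procedure taking more than 120 seconds or more than 3 insertion attempts". No readable part of the document uses this definition again.
- **Analysis.** The Sample size section says that because "time to successful intubations data are not normally distributed, we will use the Mann Whitney U test to analyse intubation times". For other data: "Categorical data such as number of intubation attempts will be evaluated for differences among the groups using the chi-square test". Failure is not named there. The chi-square test could cover it, but the plan does not say so.
- **Expectation.** The Introduction states: "We find that Box B has better ergonomics, and this will increase the rate of success of intubation".
- **Data sheet.** The visible label of the time row begins "Time for successful". Times are recorded separately for direct laryngoscopy and videolaryngoscopy. The sheet is broken in extraction, so nothing here relies on a field that seems absent.

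**The concern.** A time that ends at cuff inflation exists only if the cuff is inflated in the trachea. A run that is abandoned, or stopped after too many attempts, may have no such time. With no rule, the obvious course is to leave it out, and the test then compares only the successful runs of each box.

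That is harmless if failure is very rare. If failure is unrelated to speed, some power is lost but the mean difference is not biased. It is not harmless if one box fails more often and its failed runs are the slow ones, because omission then trims the upper tail of that box alone. The plan itself expects success to differ by box.

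Two analysts could also follow the text faithfully and get different answers, and a choice made after seeing the data could change the result.

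**Working it through.** **1. The passages side by side.** Failure has two routes.
- *Over 120 s:* the Methodology does not say that the run stops at that point. A run completed late could be timed and kept, and would then already rank above every success. This holds only if the 120 s is counted on the blade-to-cuff interval, which the plan does not state.
- *Over 3 attempts, or abandoned:* there may be no time to successful intubation at all. This is where the gap matters most.

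**2. The plan's own figure.** The 28 laryngoscopists (10.0 s, 80% power, 0.05) cannot be reproduced because no SD is given. Solving n = (SD × (1.960 + 0.842)/10)² = 28 for a paired comparison gives an SD of differences of 18.9 s. Solving 2 × (SD × 2.802/10)² = 28 per group gives 13.4 s. The point does not depend on either. Recruiting 30 leaves 2 spare, for dropouts and protocol breaches; failed intubation is not mentioned.

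**3. Assumed model (illustrative).** There are 28 pairs. Box B time = 29·exp(0.5·z₁) and Box A time = 29·exp(0.5·z₂) + 10, with correlation 0.5 between z₁ and z₂. Any run over 120 s fails. In addition the slowest 2%, 5% or 10% of Box A runs fail. The Box A cut is 29·exp(0.5·z) + 10, with z = 2.054, 1.645 and 1.282, which gives about 91, 76 and 65 s. These added failures therefore lie below 120 s and stand for failures on attempts or abandoned runs.

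**4. Mean difference when only the failed run is dropped.** The untruncated lognormal mean is 29·exp(0.125) = 32.86 s. Box B cut at 120 s has z = ln(120/29)/0.5 = 2.84 and mean 32.86 × Φ(2.34)/Φ(2.84) = 32.62 s. The Box A mean is 10 + 32.86 × Φ(z − 0.5)/(1 − p):
- 2%: 10 + 32.86 × 0.9399/0.98 = 41.51; difference 8.9 s
- 5%: 10 + 32.86 × 0.8739/0.95 = 40.23; difference 7.6 s
- 10%: 10 + 32.86 × 0.7828/0.90 = 38.58; difference 5.96 s (about 5.9 s by simulation)

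**5. Simulated Mann-Whitney power.** The two ways of omitting failures are kept apart. Power figures are good to about one or two percentage points.

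| Slowest Box A runs failing | Whole pair dropped | Only failed run dropped | All true times kept |
|---|---|---|---|
| 2% | 9.2 s, 77% | 8.9 s, 74% | 10 s, about 78% |
| 5% | 8.6 s, 77% | 7.6 s, 67% | 10 s, about 78% |
| 10% | 7.6 s, 72% | 5.9 s, 55% | 10 s, about 78% |

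With no true difference and 10% against 0% failing, the complete-pair mean difference is −2.3 s: the box that fails more looks faster.

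**6. Where the effect is small or absent.**
- *120 s limit alone:* complete-pair difference 9.9 s, power unchanged at 79%. This depends on the assumed times: 9.3 s at a median of 50 s, and 8.8 s at that median with log-SD 0.7.
- *Failures unrelated to time, 10% against 0%:* 10.0 s; power 76% against 79% when only the failed run is dropped.
- *Slowest 5% failing in both boxes, pure shift:* 10.0 s, and power is higher with failures left out.

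**The case against.** **Failures may hardly occur.** Operators need more than 5 years of intubation experience and the subject is a manikin. No failure rate is given, so the 5% and 10% one-sided scenarios are assumptions. This stands, and it limits the weight of the point.

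**The planned test copes with late completions.** A run finished after 120 s and kept at its time ranks worst anyway. This stands if the 120 s clock is the endpoint's clock. It does not help with abandoned runs or failures on attempts.

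**Attempts are recorded and tested.** Failure on attempts could be derived and compared. That is true, but it does not say what value such a run takes in the primary analysis.

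**Stronger readings that the documents do not support.**
- *The plan excludes failures.* It does not say so. The Methodology also speaks of time for intubation in general, so exclusion is an inference.
- *The gap could manufacture a benefit for Box B.* On the plan's own expectation, omission helps Box A.
- *A 10% failure rate costs both about 2.4 s and 23 points of power.* No single rule gives that pair. The smaller loss in seconds comes from dropping whole pairs, which costs about 6 points. The 23-point loss comes from dropping single runs, where the difference falls by about 4 s.
- *Equal failure rates also weaken the planned test.* Under a proportional effect with the slowest 5% failing in each box, the mean difference shrinks from 11.3 to 10.2 s. Mann-Whitney power nevertheless rises, from 58% to 63–65%.

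**Conclusion.** The point holds in a limited form and should be fixed. The plan defines failure but gives a failed run no value or rank in the primary comparison, although the endpoint exists only for successes and success is expected to differ by box. The gap mainly concerns runs that are abandoned or fail on attempts.

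If Box A fails more often and its failed runs are its slower ones, omission favours Box A. In the assumed model a 10 s difference shrinks to between 9.2 and 7.6 s when pairs are dropped, or between 8.9 and 5.9 s when single runs are dropped, for failure rates of 2% to 10%. The loss of power runs from about 1 to 23 percentage points, depending on the rate and the dropping rule. These sizes rest on assumed times, spread, correlation and failure pattern. With very rare failures, or with the 120 s limit alone at the base-case times, the effect is negligible. Confidence is medium.

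**What to change.** Before data collection, state the following.
- Every attempted run stays in the primary analysis. Any failed run, by time or by attempts, gets one common value above 120 s, and so a tied worst rank in the Mann-Whitney test.
- If a paired rank test is used instead, the common value is at least 240 s. Two successes differ by less than 120 s, while a failure at 240 s differs from any success by at least 240 − 120 = 120 s, so failure-against-success pairs take the largest ranks. A value of 120 s would not do this: a failure paired with 90 s differs by 30 s and ranks below a success pair differing by 40 s.
- Failures are reported per box, and successful runs alone are shown as a sensitivity analysis.
- The rule applies to each laryngoscopy type on the data collection sheet.
- The text says whether the 120 s limit is counted on the blade-to-cuff interval.
- Dropouts are a separate matter and are not scored as failures.

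**Cost.** One rule and one clarified definition, with no extra participants or data. The estimand becomes time with failures ranked worst, so the test also responds to a difference in failure alone. With 10% against 0% failures unrelated to time, its power is 91%, against 79% with true times. If failures are similar in both boxes, power is lost: about 77% against 84% with failures left out (slowest 5% in each).
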